2.2. Secondary Objectives and Outcomes

Secondary objectives:

- To compare the clinical course of participants in terms of antibiotics prescribed up to day 28, duration and burden of LRTI symptoms, re-consultations, imaging performed, illness deterioration (hospitalization, complications, all-cause mortality), referral for and number of cancer diagnoses in review of medical records up to day 60, and spontaneously reported unintended events detected up to day 60.
- To assess participants' satisfaction with the index consultation.

Secondary outcomes:

1) Outcomes from the LRTI symptom diary:

Participants will be asked to complete a validated LRTI symptom diary every day from the day of index consultation (day 0) to day 21¹⁸. The recorded items include the following six symptoms of LRTI: cough, dyspnea, sputum production, well-being, sleep disturbance, and activity disturbance. The participants are asked to consider how bad each symptom has been over the past 24 hours by scoring each symptom on a 7-point Likert scale (0 = no problem, 1 = very little problem, 2 = slight problem, 3 = moderate problem, 4 = bad problem, 5 = very bad problem, and 6 = as bad as it could be). Moreover, the diary contains a social domain on cancellation of work-related or leisure activities. Only on the day of the index consultation (day 0) the diary will incorporate a question on participants' satisfaction with the consultation assessed on a 5-point Likert scale (very dissatisfied (1) to very satisfied (5)).

- 1.1) Daily total LRTI symptom score, calculated as the sum of the scores for six symptoms
(minimum 0 – maximum 36) (mean/median).
- 1.2) The number of days with symptoms rated as “moderate problem” or worse by the participant (at least one item with a score of 3 or above) (mean/median).
- 1.3) Number of days participants signed in sick/cancelled work-related activities or cancelled leisure activities (mean/median).

- 1.4) Proportion of participants who were satisfied or very satisfied (4 or 5) with the index consultation.

Outcomes 1.1, 1.2 and 1.3 from the LRTI symptom diary will be calculated for each participant every day from day 0 until the participant has scored 0 for every item, whichever comes first, or up to a maximum of 21 days.

2) Outcomes from participants' shared medication records (i.e., FMK) and on type of prescription:

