3.2. Randomization and Blinding

The unit of randomisation is the patient. Participants will be randomized 1:1 to either Usual Care or +FLUS group. Each general practitioner will be provided with a pile of sequentially numbered opaque sealed envelopes (SNOSE)¹⁹. The SNOSE piles will be prepared by a remote independent researcher, using permuted block randomization to ensure similar enrolment in both groups. Different block sizes will be used to prevent the allocation sequence from being anticipated. Details on block sizes and list lengths are unavailable to general practitioners who enroll patients and assign interventions.

Owing to the type of intervention, participants and GPs are not blinded. However, members of the research team involved in obtaining or analysing data (outcome assessors and data analysts) will be blinded to the allocation until data analyses have been finalised.

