5.2. Lost to follow-up and missing data

In the case of missing data on the primary endpoint, the GP who enrolled the participant will be contacted to clarify if antibiotics were prescribed at the index consultation. If clarification is not obtained, we will consider it as if antibiotics were prescribed at the index consultation. We expect that the use of an e-CRF for GPs to complete at the time of index consultation will keep missing data on the primary outcome at a minimum. We expect that only observed data will be included in the secondary analyses.

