5.5. Secondary Outcomes

Table 1: All measured outcomes at different endpoints with type of data and planned statistical analyses are listed below

Outcome	Unit/options	Endpoint (days from index consultation)					Type of data	Statistical analyses
		0	0-21	7	28	60		
Secondary outcomes								
Daily total LRTI symptom score	0-36		X				Ordinal	Mean/Median, 95% CI, Chi ² or Fischer's exact
Duration of symptoms rated 3 or above	Days		X				Ratio	Mean/Median, 95% CI, Independent samples t-test/Mann Whitney U
Cancelled work related activities	Days		X				Ratio	Mean/Median, 95% CI, Independent samples t-test/Mann Whitney U
Cancelled leisure activities	Days		X				Ratio	Mean/Median, 95% CI, Independent samples t-test/Mann Whitney U
Satisfied or very satisfied (4 or 5) with index consultation	1 (very dissatisfied), 2 (dissatisfied), 3 (nor dissatisfied or satisfied), 4 (satisfied), 5 (very satisfied)	X					Nominal	Proportions, Chi ² or Fischer's exact
Type of antibiotic prescription at index consultation	Immediate/Delayed	X					Nominal	Proportion, RR, 95% CI, Chi ² or Fischer's exact
Antibiotic prescribed within 7 days after index consultation	Yes/No			X			Nominal	Proportion, RR, 95% CI, Chi ² or Fischer's exact
Antibiotic prescribed within 28 days after index consultation	Yes/No				X		Nominal	Proportion, RR, 95% CI, Chi ² or Fischer's exact
Reconsultation within 28 days after index consultation	Yes/No				X		Nominal	Proportion, RR, 95% CI, Chi ² or Fischer's exact
Hospitalization within 28 days after index consultation	Yes/No				X		Nominal	Proportion, RR, 95% CI, Chi ² or Fischer's exact
Complication within 28 days after index consultation	Yes/No				X		Nominal	Proportion, RR, 95% CI, Chi ² or Fischer's exact

Referred for suspicion of cancer (any) within 60 days after index consultation	Yes/No				X	Nominal	Proportion, RR, 95% CI, Chi ² or Fischer's exact
Diagnosed with cancer (any) within 60 days after index consultation	Yes/No				X	Nominal	Proportion, RR, 95% CI, Chi ² or Fischer's exact
All-cause mortality within 60 days after index consultation	Yes/No				X	Nominal	Proportion, RR, 95% CI, Chi ² or Fischer's exact
Adverse event within 60 days after index consultation	Yes/No				X	Nominal	Proportion, RR, 95% CI, Chi ² or Fischer's exact

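### Day counts from the symptom diary, analysed on observed entries alone, are biased low when diaries are abandoned, and can differ falsely between arms if abandonment differs

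*SAP*

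**What the plan says.** Section 2.2 defines two diary outcomes as day counts. Outcome 1.2 is the number of days on which at least one item scores 3 or more, listed in section 5.5 as "Duration of symptoms rated 3 or above". Outcome 1.3 is "Number of days participants signed in sick/cancelled work-related activities or cancelled leisure activities". Both are calculated "from day 0 until the participant has scored 0 for every item, whichever comes first, or up to a maximum of 21 days".

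The table in section 5.5 gives the analysis of these counts as "Mean/Median, 95% CI, Independent samples t-test/Mann Whitney U". On missing data, section 5.2 gives the primary outcome a specific rule: ask the GP and, failing an answer, count antibiotics as prescribed. For everything else it says "We expect that only observed data will be included in the secondary analyses". On blinding, section 3.2 says "Owing to the type of intervention, participants and GPs are not blinded", so the people filling in the diary know their arm.

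**The concern.** A diary can end in three ways: the participant reaches all-zero scores, day 21 arrives, or the participant stops filling it in. The SAP provides for the first two only. A participant who recovers on day 5 and one who gives up on day 5 while still ill can then have the same recorded count, although the second count is only a lower bound.

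The rule in section 5.2 can be carried out in two ways. One is to add up whatever entries exist. The other is to leave out participants with unfinished diaries. The SAP does not say which, so the choice could be made after the data are seen. Neither is neutral, because the first scores every unfilled day as symptom free and the second removes long illnesses more often than short ones.

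Duration and burden of symptoms form part of the secondary objective. If completion differs between arms that know their allocation, that difference is carried into the comparison of illness days. It could produce a difference that does not exist or hide one that does.

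**Working it through.** **The plan's figures.** The SAP states no figure for the diary outcomes, so there is none to reproduce. Its sample size (170 per arm before inflation, which does reproduce at two-sided 5% and 80% power) concerns the primary outcome. The only plan input used here is 195 per arm (section 3.3).

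**Assumed inputs, not in the SAP.** True symptom days follow a gamma shape (shape 2.5), capped at the 22 diary days 0 to 21, with target means of 7 to 11. Abandoners stop on a day uniform on 1 to 14, unrelated to their symptoms. There is no true difference between arms.

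**Formula.** Let T be a participant's true symptom days and S the last diary day of an abandoner. Summing as recorded gives min(T, S), which can never exceed T. If a is the abandonment rate and L the mean number of days lost per abandoner:
- understatement in an arm = a × L
- false arm difference with no true effect = (a₁ − a₀) × L

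**Equal abandonment.** At target mean 9 the true mean after capping is 8.9. With 20% abandonment in both arms the observed mean is 8.2. Both means are too low, the arm difference is zero and the type I error stays near 5%.

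**15% versus 30%, target mean 9, counts summed as recorded.**
- Observed means are 8.36 and 7.86, a difference of 0.50 day, so L = 0.50 / 0.15 = 3.3 days.
- Cross-check: 0.20 × 3.3 = 0.7 day, and 8.9 − 0.7 = 8.2, as above.
- The standard error is 0.53, so the shift is 0.50 / 0.53 = 0.94 standard errors, and P(|Z + 0.94| > 1.96) ≈ 0.156. Simulation also gives about 16%.

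**Range over target means 7 to 11.**

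| Handling | Abandonment | False difference | Type I error |
|---|---|---|---|
| Summed as recorded | 5% vs 15% | 0.2 to 0.5 day | 7% to 12% |
| Summed as recorded | 15% vs 30% | 0.3 to 0.7 day | 12% to 24% |
| Unfinished diaries dropped | both scenarios | 0.1 to 0.3 day | 6% to 9% |

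The dropped-diary row also assumes that the all-zero day falls about 2 days after the last day rated 3 or above. At 15% versus 30% and mean 9, completers average 8.65 and 8.40, a difference of 0.25 day. In every row the arm with more abandonment appears to have the shorter illness.

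**A different model.** With negative binomial days (true means about 8.0 and 11.5) and stopping spread over days 1 to 21, summed counts at 10% versus 20% give 0.18 and 0.38 day, with type I error 7.5% and 9.1%. Mann-Whitney results are close to those of the t-test.

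**Outcome 1.3.** If cancelled-activity days average only 2 to 4 and fall early (also an assumption), 15% versus 30% gives a false difference of 0.02 to 0.11 day and type I error of 5.4% to 7.1%.

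**The case against.** The strongest reply is that section 5.2 states an expectation, not an algorithm. It nowhere says that unfilled days are scored as symptom free, and it could mean that unfinished diaries are left out. That is correct, and a reader should not infer that the SAP has chosen the summing rule. It roughly halves the effect in the mean-9 example (0.25 against 0.50 day) but does not remove it.

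Second, the sizes rest on assumed rates. The only attrition figure in the SAP is a trial-level maximum of 10% in section 3.3, and 15% versus 30% lies well above it. Nothing in the document says that completion will differ by arm. This stands too: open allocation makes a difference possible, but the SAP does not support saying that one will occur. The 5% versus 15% scenario averages to that 10% and is the more cautious guide.

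Third, a reader might infer that these outcomes exist to show that less prescribing does not prolong illness, which would raise the stakes. The SAP does not say so. It describes a superiority trial, and its secondary objective is to compare the clinical course.

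Finally, the primary outcome is untouched, since it has its own missing-data rule. This is why the point ranks as something the plan should change and not as a threat to the trial's main conclusion.

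**Conclusion.** The point holds in this form: the observed-data rule, applied to day counts with no provision for abandoned diaries, biases those counts downward under either way of carrying it out. The understatement follows by arithmetic whenever a diary is abandoned with symptom days still to come and the entries are summed. A false arm difference is conditional on abandonment differing between arms. Its size then depends on the gap in abandonment and on illness length, as tabulated above, and all of those inputs are assumptions. Abandonment unrelated to symptoms is one of them: the loss is smaller if participants stop because they feel better, and larger if the sickest stop.

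The weight falls on outcome 1.2. For 1.3 the effect is small if its mean is only a few days, so the two should not be presented as equally exposed.

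**What to change.** Amend section 5.2 for outcomes 1.2 and 1.3:

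- After an all-zero entry, set the remaining days up to day 21 to 0.
- Where a diary stops without an all-zero entry, treat the later days as missing, not as symptom free.
- Estimate mean days per arm and their difference by multiple imputation of the missing daily yes/no indicators, done by arm and using earlier diary scores and baseline variables. A likelihood-based mixed logistic model is an alternative, provided that fitted probabilities are averaged over the random effects before being summed over days 0 to 21.
- Give a bootstrap 95% confidence interval; section 5.1 already names the bootstrap.
- Report diary completion by arm, and keep the raw observed sums as a sensitivity analysis.

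An unweighted GEE should not be relied on. It is not generally valid under missing-at-random, and here missingness depends on past state, because recovered diaries are completed with zeros while symptomatic ones go missing. In the gamma simulation at 30% abandonment, an independence GEE still gave 8.67 against a true 8.85, a shortfall of 0.18 day.

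The cost is SAP wording and modest programming, with no new data. The drawback is reliance on a missing-at-random assumption, which is still weaker than assuming that every unfilled day is symptom free.

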5.3. Data validation

Data will be examined for missing values and outliers. Measures of central tendency and dispersion for continuous study parameters will be portrayed. Extreme or unexpected values will be examined individually for authenticity and data discrepancies addressed where appropriate.

5.4. Primary Outcome

The primary outcome data will be displayed in a 2x2 table comparing the dichotomous outcome variable of antibiotics prescribed at the index consultation. The primary analyses will be the proportion of patients prescribed an antibiotic at the index consultation (day 0) in the two groups. The primary analyses will also include the risk ratio (RR) presented with a 95% confidence interval (95% CI). We will test if there is a difference in the risk of having antibiotics prescribed at the index consultation between the two groups. We will consider the variation between GPs as part of the primary analyses.

Outcome	Unit/options	Endpoint (days from index consultation)	Type of data	Statistical analyses
---------	--------------	---	--------------	----------------------

		0	0-21	7	28	60		
Primary outcome								
Antibiotics prescribed at index consultation	Yes/No	X					Nominal	Proportions, RR, 95% CI, Chi ²

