3.3. Sample Size

Based on previous audit projects in general practice in Denmark²⁰⁻²¹, a Danish study by Holm et al.⁹ and a Dutch study on reducing antibiotic prescribing in patients with LRTI²², we assume to detect a 15% decrease in antibiotic prescribing in patients with LRTI from 50% (usual care) to 35% (+FLUS). Using a 5% significance level and a power of 80% a total of 340 patients with 170 trial participants in each arm is needed. We assume withdrawal or discontinuation by a maximum of 10% of participants²². Furthermore, we increase the sample size by 5% to account for covariates in the analyses. Consequently, we plan to include a total of 390 trial participants (195 in each arm). Each GP is encouraged to include a minimum of 10 participants to account for the individual effect of FLUS on antibiotic prescribing at a GP level.

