4.2 Baseline characteristics

Patients

Date of enrolment, age, sex (provided from social security number), comorbidities, smoking status. Participants' symptoms and signs of acute LRTI, the results of physical examination and any POCT performed as part of usual care (e.g., CRP) in both groups. FLUS pathological findings will be reported for the +FLUS group.

General practitioners

Age, sex, region of Denmark, type of clinic, seniority as a GP, experience with POCUS, experience with FLUS, type of ultrasound device (hand-held, laptop or fixed), ultrasound brand and model, transducer(s) used, and baseline antibiotic prescribing.

Baseline characteristics	Unit/options	Endpoint (days from index consultation)					Type of data	Statistical analyses
		0	0-21	7	28	60		
General practitioners								

Age	Years	X				Ratio	Mean/Median, 95% CI
Sex	Male/Female	X				Nominal	Proportions
Region of Denmark	North/Central/Southern /Zealand/Capitol	X				Nominal	Proportions
Type of clinic	Solo/Partnership/ Collaboration/Other	X				Nominal	Proportions
Seniority as a GP	Years	X				Ratio	Mean/Median, 95% CI
Experience POCUS	Years	X				Ratio	Mean/Median, 95% CI
Experience FLUS	Years	X				Ratio	Mean/Median, 95% CI
Type of ultrasound machine system	Hand-held, Laptop, Stationary	X				Nominal	Proportions
Number of transducers available	Number	X				Ratio	Mean/Median, 95% CI
Type of transducer used for FLUS	Linear/curved/phased-array/other	X				Nominal	Proportions
Baseline antibiotic prescribing	Defined as daily doses per 1000 patients per year	X				Ratio	Mean/Median, 95% CI
Patients							
Date of enrolment	Date	X				Ordinal	Used to calculate age at date of enrolment
Date of birth	Date	X				Ordinal	Used to calculate age at date of enrolment
Age	Years	X				Ratio	Mean/Median, 95% CI, Independent samples t-test/Mann Whitney U
Sex	Male/Female	X				Nominal	Proportions, Chi ² or Fischer's exact
List of comorbidities	Present/not present	X				Nominal	Proportions, Chi ² or Fischer's exact
Smoking status	Smoker/former smoker/never-smoker	X				Nominal	Proportions, Chi ² or Fischer's exact
List of symptoms	Present/not present	X				Nominal	Proportions, Chi ² or Fischer's exact
List of clinical findings	Present/not present	X				Nominal	Proportions, Chi ² or Fischer's exact
List of point-of-care tests	Performed/not performed	X				Nominal	Proportions, Chi ² or Fischer's exact

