5.7 Statistical software

The PI, who is blinded to group allocation, will perform the statistical analyses in Stata Version 17 according to the SAP. The PI and coauthors remain blinded until after the analyses have been performed, and conclusions are drawn.

6. Implementation of Analysis Plan

Any revision of the SAP will appear from version number. The SAP will be uploaded to ClinicalTrials.gov NCT06210282 before enrolment of the last participant.

7. References

- 1: [https://www.who.int/news-room/fact-sheets/detail/antibiotic-resistance \(01.03.2019\)](https://www.who.int/news-room/fact-sheets/detail/antibiotic-resistance).
- 2: Bell BG, et al. *A systematic review and meta-analysis of the effects of antibiotic consumption on antibiotic resistance*. BMC Infectious Diseases, 2014. 14:13.
- 3: <https://www.danmap.org/-/media/arkiv/projekt-sites/danmap/danmap-reports/danmap-2017/danmap2017.pdf?la=en> (01.03.2019)
- 4: Aabenhus R, et al. *Clinical indications for antibiotic use in Danish general practice: results from a nationwide electronic prescription database*. Scandinavian journal of primary health care. 2017;35(2):162-69.
- 5: Aabenhus R, et al. *Antibiotic prescribing in Danish general practice 2004-13*. The Journal of antimicrobial chemotherapy. 2016;71(8):2286-94.
- 6: www.nice.org.uk, Clinical guideline [CG191], “Pneumonia in adults: diagnosis and management” (06.02.2019)
- 7: Holm A, et al. *Procalcitonin versus C-reactive protein for predicting pneumonia in adults with lower respiratory tract infection in primary care*. Br J Gen Pract. 2007;Jul;57(540):555-60.

8: Little P, et al. *Effects of internet-based training on antibiotic prescribing rates for acute respiratory-tract infections: a multinational, cluster, randomised, factorial, controlled trial.* Lancet. 2013;Oct 5;382(9899):1175-82.

9: Holm A, et al. *Aetiology and prediction of pneumonia in lower respiratory tract infection in primary care.* Br J Gen Pract. 2007;Jul;57(540):547-54.)

10: Llamas-Alvarez AM, et al. Accuracy of Lung Ultrasonography in the Diagnosis of Pneumonia in Adults: Systematic Review and Meta-Analysis. *Chest*, 2017. 151(2): p. 374-382.

11: Long L, et al., Lung ultrasound for the diagnosis of pneumonia in adults: A meta-analysis. *Medicine (United States)*, 2017. 96(3): p. no pagination.

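### Section 5.4 promises to consider variation between GPs in the primary analysis, but the only test it names does not use GP

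*SAP*

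**What the plan says.** Section 5.4 sets out a 2x2 table of arm by antibiotic prescription, the two proportions, an RR with 95% CI and a test of the difference. It closes with "We will consider the variation between GPs as part of the primary analyses". The primary outcome row of its table reads "Proportions, RR, 95% CI, Chi" (chi-square). Neither the prose nor the row says how GP enters the test, the RR or the interval.

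Other sections show that GP matters to this design:

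- Section 3.2: patients are the unit of randomisation, and each GP holds a separate pile of numbered envelopes, prepared "using permuted block randomization to ensure similar enrolment in both groups".
- Section 3.3: GPs are asked to "include a minimum of 10 participants to account for the individual effect of FLUS on antibiotic prescribing at a GP level". It also says "Furthermore, we increase the sample size by 5% to account for covariates in the analyses", without naming the covariates.
- Section 4.2: each GP's baseline antibiotic prescribing is recorded.

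No other section supplies the method. Section 5.1 mentions the bootstrap for non-normality only, section 5.6 lists patient subgroups, and section 5.7 names the software and says the PI "will perform the statistical analyses in Stata Version 17 according to the SAP".

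**The concern.** The outcome is a decision made by the GP, so prescribing can be expected to differ between GPs. The prose of 5.4 promises to deal with this, but a chi-square on one pooled table cannot. If patients are blocked within GP, differences between GPs largely cancel from the comparison of arms. The pooled test still counts them as noise, so its p-value is too large on average and some power is lost.

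The primary p-value and interval are also not fixed in advance. Several methods would satisfy a promise to consider GP variation, and they need not agree. In simulations on the assumptions listed under working (GP SD 0.5 or 1.0, FLUS effect SD 0, 0.5 or 0.8), the crude chi-square, a GP-stratified test and a test on within-GP differences did not all agree on significance in 5 to 14% of trials at the planned effect. Blinding the analyst hides the direction of the result but not the p-value, so it does not settle the choice.

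**Working it through.** **The plan's own figure.** Inputs from 3.3: 50% against 35%, 5% level, 80% power. With pooled variance, two-sided and no continuity correction:

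n per arm = [z(0.975)·√(2·0.425·0.575) + z(0.80)·√(0.50·0.50 + 0.35·0.65)]² / 0.15² = [1.960·0.6991 + 0.8416·0.6910]² / 0.0225 = 169.3, so 170 per arm and 340 in total.

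This reproduces the SAP (a one-sided test would need 134 per arm). The allowances give 340 × 1.15 = 391, or 340 × 1.10 × 1.05 = 392.7, close to the planned 390. Power is 80.2% at 170 per arm and 85.3% at 195. The formula has no GP term.

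**Why the crude test is conservative.** Under no effect with p = 0.5, the pooled test uses the variance p(1−p) = 0.25. With balance within GP, the difference between arms varies only through the within-GP part, 0.25·(1−ρ), where ρ = Var(GP proportion)/0.25. The approximate true size is then 2·Φ(−1.96/√(1−ρ)). For normal GP intercepts on the logit scale:

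| GP logit SD | Var(GP proportion) | ρ | Size |
|---|---|---|---|
| 0.5 | 0.0140 | 0.056 | 4.4% |
| 0.8 | 0.0310 | 0.124 | 3.6% |
| 1.0 | 0.0434 | 0.174 | 3.1% |

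**Simulation, common FLUS effect.** Assumed, because the SAP does not give them: 39 GPs, 390 patients, permuted blocks of 2, 4 and 6 within GP, and the SDs. There were 20,000 trials per setting (standard error about 0.15 points for size, 0.25 for power). The Cochran-Mantel-Haenszel (CMH) statistic is [Σ(x₁ − n₁t/n)]² / Σ[n₁n₀t(n−t)/(n²(n−1))], summed over GPs. Here x₁ is prescriptions in the FLUS arm, t is all prescriptions, and n₁, n₀ and n are patients per arm and in total at that GP.

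| GP logit SD | 0 | 0.5 | 0.8 | 1.0 |
|---|---|---|---|---|
| Size, 10 per GP: crude | 5.0% | 4.6% | 3.8% | 3.1% |
| Size, 10 per GP: CMH | 5.1% | 5.3% | 5.3% | 5.0% |
| Power, 10 per GP: crude | 85.4% | 85.8% | 86.4% | 87.3% |
| Power, 10 per GP: CMH | 85.2% | 86.7% | 88.8% | 90.7% |
| Power, 9 per GP (351): crude | 81.3% | 82.3% | 83.2% | 83.2% |
| Power, 9 per GP (351): CMH | 80.8% | 82.9% | 85.7% | 87.3% |

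With uneven enrolment (1 to 28 per GP), crude size is 4.8 / 4.3 / 3.8 / 3.0%, and CMH changes power by −1.0 / +0.3 / +2.1 / +3.1 points. For SD 0.5 to 1.0 the gain from CMH therefore runs from 0.3 points to 87.3 − 83.2 = 4.1 points.

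**If the piles are not blocked within GP** (simple allocation assumed), the crude test holds 4.8 to 5.2%, and CMH changes power by −3.7 / −1.4 / +0.8 / +2.4 points.

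**If the FLUS effect varies by GP** (GP SD 0.5, inference to GPs in general), size is as follows, equal / uneven enrolment:

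| SD of GP-specific log odds ratio | Crude | CMH | GP-clustered RR, t on 38 df |
|---|---|---|---|
| 0.3 | 5.0 / 5.2% | 5.7 / 5.9% | 4.8 / 5.5% |
| 0.5 | 5.4 / 6.6% | 6.4 / 7.6% | 4.6 / 5.5% |
| 0.8 | 7.1 / 9.8% | 8.3 / 11.3% | 4.8 / 5.5% |

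An SD of 0.8 is large: exp(±1.96 × 0.8) puts 95% of GP-specific odds ratios between 0.21 and 4.8 times that of the median GP.

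**The case against.** The opening of section 5 allows a priori analyses to be defined in the protocol or in the SAP, so the method might stand in the protocol, which is not at hand. That is fair as far as it goes. However, 5.4 names a test that does not do what its own prose promises, and 5.7 ties the analysis to the SAP, so the text needs correcting wherever else the method may appear.

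A reader might infer that ignoring GP inflates the false-positive rate as in a cluster trial, or that the sample size is too small. The SAP does not support either. Patients are randomised individually from piles held by each GP, so a cluster design effect does not apply. With a common FLUS effect the crude test errs on the cautious side, and its simulated power stays above 80% even with 10% of patients removed.

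A reader might also infer inflation from the GP-level effect mentioned in 3.3. That needs two things the SAP does not state: inference to GPs in general, and a strong spread of the FLUS effect between GPs. With equal enrolment the crude test is still at 5.4% for an effect SD of 0.5. This supports a sensitivity analysis, not a claim that the primary test is invalid.

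Finally, every simulated figure rests on an assumed GP count, block sizes, enrolment pattern and SDs. This stands. The mismatch within 5.4 does not depend on them.

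**Conclusion.** The point holds and should be acted on. The promise in 5.4 and the test named there do not match, and no other section of the SAP closes the gap. That part rests on the text alone.

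The numerical consequence is modest. If piles are blocked within GP (the natural reading of 3.2, though not stated outright) and FLUS has a common effect, the crude chi-square has a size of about 3 to 4.6% and loses about 0.3 to 4 points of power to a GP-stratified test, for a GP logit SD of 0.5 to 1.0. Type I error is not inflated in that setting, and the planned 80% power is not in danger.

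Only if the FLUS effect varies strongly between GPs and the conclusion is meant for GPs in general do both the crude test and CMH exceed 5%: about 7 to 11% at an assumed log-odds SD of 0.8.

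**What to change.** In the prose and the primary outcome row of 5.4:

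1. Name as primary the Cochran-Mantel-Haenszel test stratified by GP, two-sided at 5%, with the Mantel-Haenszel RR and its 95% CI.
2. Keep the crude 2x2 chi-square and crude RR as supporting results.
3. Add a sensitivity analysis: an RR with GP-clustered standard error and a t reference on (number of GPs − 1) degrees of freedom. With a normal reference its simulated size was 5.2 to 6.3%.

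The cost is wording only: no new data or patients, and standard Stata commands. The downside is that GPs whose patients all fall in one arm add nothing to the stratified test. In the uneven enrolment pattern, 33.9 of 39 GPs were informative on average. This costs about 1 point of power if GPs do not differ, and up to about 3.7 points if the piles are not blocked within GP. One sentence in 3.2 saying whether each pile is its own blocked list would show which cost applies, without disclosing block sizes.
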